#### **Phase 3**

##### **Specific Aims for Phase 3 Research:**

**3.** Examine the effects of RISE on WVs’ (n=60-68) individual psychosocial outcomes (e.g., empowerment, self-efficacy, health symptoms, service use, and quality of life) in an RCT that compares RISE to an information/referral condition.

Sub-aim **3a.** Evaluate the feasibility and acceptability of RISE in the context of the RCT.

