
#### **Randomization and intervention delivery.**

Patients (women veterans) will be randomized within site to condition. Randomizing providers to only one condition risks that RISE delivery skill may be imbalanced across conditions. We recognize that when providers are involved in both conditions, provider learning may blend into both conditions (e.g., use of motivational interviewing (MI) skills for selecting RISE modules influencing information/referral delivery). We anticipate the risk of the latter is limited because the RISE materials explicitly prompt MI strategies whereas the comparison condition does not. Thus, providers will deliver both interventions. This will also allow providers to contrast RISE with a more minimal intervention when providing perspectives on feasibility and acceptability. We will record all sessions in both conditions and we will assess and monitor condition fidelity and treatment differentiation using adherence checklists that contain the critical RISE and the information/referral elements. We will use software to conduct a simple randomization process to assign women to an intervention condition. The individuals conducting the informed consent will not be aware of the participants assigned condition until the participant has completed the signed informed consent and HIPAA Waiver (assignment of condition will be in a sealed envelope). Although we had considered using stratified randomization to balance conditions on patient characteristics (e.g., age, IPV frequency), there is no a priori reason to expect such factors to significantly influence our primary outcomes, although we will include demographic/relationship factors as covariates in our analyses if demographic/relationship characteristics differ across groups (see Quantitative Data Analysis Plan below). During COVID-19, following the participant's consent, the study team will email intervention materials to the participant for use during their same day intervention session.

**Information/referral intervention.** The information/referral condition is referred to as the "Make the Connection" intervention in the informed consent form. The title of this intervention reflects some of the underlying purpose of the information/referral condition, which is to make the connection between IPV and

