**Female VHA Patient Assessments.** Data collection takes place throughout the study and is modeled after a prototypical Hybrid 1 trial . We will administer a full battery of psychosocial assessment at pre-treatment, post-treatment assessment (i.e., 10-weeks post enrollment), and 1 month follow-up (i.e., 14 weeks post-enrollment) described below under “Measures.” Participants in the RISE condition will also complete four brief measures of empowerment, self-efficacy, patient activation and valued action at the beginning of each RISE session. At the posttreatment and follow-up assessment, patients will complete a brief audio-recorded semi-structured interview about their experiences with their respective intervention. The post-treatment and follow-up assessments will either be conducted by phone or in person, depending on the participant’s preference (thus allowing for them to determine what is most safe and preferable for them). Women will be compensated with

\$25 for completing the pre-treatment assessment. Upon completion of the post-treatment assessment, women will receive \$50 in cash or by check for their time and participation. Upon completion of the follow-up assessment, women will receive a \$75 in cash or by check for their time and participation. A timeline of all measures is available below in Table 4.

Table 4. Timeline of Assessments	Pre	10-week	14-week
Demographics (age, race, sexual orientation, # deployments)	X		
Demographics (relationship status, housing status)	X	X	X
Personal Progress Scale	X	X	X
Patient Activation Measure- Short Form (PAM-13)	X	X	X
Valued Living Questionnaire (VLQ)	X	X	X
Center for Epidemiological Studies- Depression Scale (CES-D)	X	X	X
Health Service Use	X	X	X
The Conflict Tactics Scale-Revised (CTS-2)	X	X	X
PTSD Checklist for DSM-5 (PCL-5)	X	X	X
Patient Health Questionnaire- 15 (PHQ-15)	X	X	X
12-item Short Form Survey (SF-12)	X	X	X
Safety Behaviors Checklist (SBC)	X	X	X
Connor-Davidson Resilience Scale (CD-RISC 25)	X	X	X
Client Satisfaction Questionnaire 8 (CSQ-8)	X	X	X
Depression Anxiety Stress Scale- (DASS)	X	X	X
Coping Strategy Inventory-Short Form (CSI-SF)	X	X	X
Acceptability		X	X
IPV-Related Head Injury	X		

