### Quantitative Data Analyses (Aim 3)

We will conduct multilevel longitudinal data analyses to examine change in psychosocial outcomes. Time will be coded as 0, 1, and 2 respectively for pretreatment, posttreatment, and 1-month follow-up; therefore, the Level-1 intercept will represent initial status and the Level-2 time coefficient will represent change over time. We will also evaluate a model using linear and quadratic polynomial contrasts and orthogonal contrasts to evaluate non-linear (i.e., non-constant) change. We will add a dummy-coded intervention variable (RISE vs. information/referral condition) as a predictor of the Level-1 change parameters (initial status and change over time) to evaluate the treatment x time interaction (i.e., does group membership moderate change in the outcomes?). This analytic strategy will produce effective and efficient tests of change in outcomes, even in the presence of attrition, and provides us with flexibility to assess and adjust for control variables, if needed (e.g., age, IPV frequency). We will calculate effect size estimates and 95% confidence intervals, which produce an estimate of  $d$  from multilevel analyses that is comparable to  $d$ 's produced using traditional methods (e.g., repeated measures ANOVA). To examine the range of effect sizes that might be reasonable to expect in a future trial, we will calculate effect sizes and 95% confidence intervals for all of our primary and secondary outcomes.

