The study will incorporate a 2 x 3 (Condition: RISE vs. information/referral x Time: pretreatment, post, and 1-month follow-up) mixed-factorial multi-measurement design producing  $N=60 \times 3$  time points = 180 measurement observations (or up to  $N=68 \times 3$  timepoints = 204). The intervention in this study is a difference over and above standard care (not in isolation), so it is expected that the effect will be modest ( $d=.5$ ,  $f^2=.15$ ,  $PV=.1$ ). Traditional approaches to repeated measures can thus be used to assess power. However, the design affords two alternate methods. The interaction term from the multilevel model will have 118 degrees of freedom, given the study design, which is more than sufficient to render a power = .95 for the primary outcomes. A simulation was also conducted leveraging the inputs from the prior studies, assuming a modest effect size, to determine power. In all simulated conditions, power is estimated  $>.80$  for primary outcomes. Consistent with the American Statistical Association recommendations, we will examine effect sizes and 95% confidence intervals, along with p-values in our tests.

We will assess the feasibility and acceptability of RISE and the comparison condition by looking for consistent patterns in rates of intervention attendance (i.e., number of RISE sessions attended) and reasons for RISE termination. We will examine the acceptability of both interventions using data from the CSQ-8 and qualitative data from patient interviews. Provider quantitative measures of feasibility and acceptability will be primarily

descriptive in nature, including mean summary scores and proportion of participants rating the intervention as feasible and acceptable. Lower scores will indicate a need to examine a given dimension more closely. We will integrate qualitative analyses within the quantitative analyses for the purposes of expansion, development, and convergence.

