*Subjects and generalizability.* While the findings from this study will be highly informative, they will not be definitive. Our RCT design for Phase 3 provides a strong test of RISE, controlling for any spontaneous changes in outcomes (e.g., Hawthorne effect) and enabling comparison of changes observed in patient outcomes during RISE to what we observe in the information/referral condition. This increases confidence that changes observed in the RISE condition are a result of the intervention, as opposed to assessment or contact with project personnel. Generalizability will, however, be limited due to the use of only one site. The effectiveness of RISE will need to be more rigorously evaluated in a larger study with a diverse array of WVs (e.g., rural women, racial/ethnic minorities). In the likely event that RISE demonstrates effectiveness, we will submit a subsequent IIR employing a multi-site RCT that is fully powered to evaluate a range of psychosocial outcomes using an effectiveness-implementation Hybrid 2 design. This will allow us to more comprehensively evaluate RISE with a diverse array of women Veterans (e.g., rural women, racial/ethnic minorities) and providers while also

May 12th, 2020

evaluating implementation strategies. Additionally, this study focuses on refining and evaluating RISE for WVs. Although we will not be able to confidently generalize results to male patients or non-VHA settings, the findings will likely hold implications for men and could be applied to other health care settings in future studies.

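### The plan claims power for primary outcomes but names no primary score or contrast and sets no alpha, multiplicity rule or success criterion, although it foresees an effectiveness conclusion

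*Combined protocol and SAP*

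**What the plan says.** The combined protocol and SAP refers to primary outcomes in two sections.

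- **Randomization and intervention delivery**, explaining why stratification was not used: "there is no a priori reason to expect such factors to significantly influence our primary outcomes".
- **Quantitative Data Analyses (Aim 3)**: "we will calculate effect sizes and 95% confidence intervals for all of our primary and secondary outcomes". The same section says the interaction term has 118 degrees of freedom, "which is more than sufficient to render a power = .95 for the primary outcomes", and that simulated power exceeds .80 for them.

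The nearest thing to an outcome list is the Phase 3 aim, which speaks of "individual psychosocial outcomes (e.g., empowerment, self-efficacy, health symptoms, service use, and quality of life". These are examples of domains, without instrument, time point or ranking. Table 4 and the Measures section list the scales unranked.

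The analysis is a multilevel model with time coded 0, 1, 2 and a treatment x time interaction. A further model uses polynomial and orthogonal contrasts to look for non-linear change. On inference the plan says only that "we will examine effect sizes and 95% confidence intervals, along with p-values in our tests". It gives no alpha, order of testing or adjustment.

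On use of the results, the paragraph on subjects and generalizability (section 4.d) says the findings will not be definitive. It then continues: "In the likely event that RISE demonstrates effectiveness, we will submit a subsequent IIR".

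**The concern.** A power statement and an effectiveness conclusion both need a designated test, and the plan has neither a designated score nor a decision rule. Followed as written, it lets the primary result be picked after the comparative data are seen, from a dozen or more scales and more than one form of time contrast. The error rate attached to a conclusion that RISE works is then no longer that of a single test. Unadjusted 95% intervals on each scale do not help, because a scale whose interval excludes zero can be picked out in the same way.

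The choice is not obvious from context. The conceptual model treats empowerment, self-efficacy and patient activation as the route to better health, safety and quality of life, while the Phase 3 aim lists both kinds of measure side by side as outcomes. At stake is whether the anticipated multi-site trial would rest on a pre-stated result or on whichever scale did best.

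**Working it through.** **1. The plan's own figure.** The stated power of .95 can be reproduced from the plan's PV = .1. This gives f² = .1/.9 = .111. With one numerator and 118 denominator degrees of freedom, λ = .111 × (1 + 118 + 1) = 13.3. A single unadjusted test at .05 then has power .952. The plan's other effect sizes give .988 (f² = .15) and .775 (d = .5, so f² = .0625). This does not endorse the power figure, since it treats the data as about 120 independent observations. It shows that the stated power fits one test at .05 with no multiplicity adjustment.

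**2. How many scales.** Table 4 marks 14 scored instruments at all three visits: Personal Progress Scale, PAM-13, VLQ, CES-D, Health Service Use, CTS-2, PCL-5, PHQ-15, SF-12, SBC, CD-RISC, CSQ-8, DASS and CSI-SF.

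- The General Self-efficacy Scale is in Measures but not in Table 4. Adding it gives 15.
- CSQ-8 is described in Measures as given only after treatment (Table 4 also marks it at baseline), and the analysis section uses it for acceptability. CTS-2 is described as characterising the sample's past-year IPV. Removing both gives 12, or 13 with the General Self-efficacy Scale.

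The plausible range is therefore 12 to 15.

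**3. Assumptions not in the documents.** Two-sided alpha of .05 (suggested by the 95% intervals and by step 1), no true effect on any scale, one treatment x time test per scale, any one significant scale read as success, and equal correlation r between test statistics. The r values are illustrative.

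**4. Chance of at least one nominally significant scale.** Under independence this is 1 − .95^k in either direction, and 1 − .975^k counting only results that favour RISE. Correlated values come from the equicorrelated normal model.

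| k | Direction | Independent | r = .3 | r = .5 | r = .7 |
|---|---|---|---|---|---|
| 13 | either | .487 | .42 | .33 | .24 |
| 14 | either | .512 | .44 | .35 | .25 |
| 13 | favours RISE | .280 | .21 | .17 | .12 |
| 14 | favours RISE | .298 | .22 | .17 | .12 |

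For comparison, one two-sided test at .05 carries 5% in either direction and 2.5% in RISE's favour. At the ends of the range under independence, k = 12 gives .460 and k = 15 gives .537 in either direction.

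**5. What pushes these up.** SF-12 has two subscales and CSI-SF has four second-tier ones. Counting these subscales instead of one score each turns 14 instruments into 14 − 2 + 2 + 4 = 18 scores, and 1 − .95^18 = .603 under independence. Quadratic and orthogonal contrasts would add further tests per scale.

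**6. Correcting over everything instead.** For a simple two-group comparison with 30 per arm and d = .5, power is Φ(d√(n/2) − z), with d√(n/2) = .5 × √15 = 1.94. At .05 (z = 1.96) power is .49. At .05/14 = .0036 (z = 2.91) it is .16. Naming one primary avoids that penalty.

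**The case against.** The strongest reply is that this trial is an estimation exercise. The plan says one purpose of reporting effect sizes with intervals for all outcomes is to inform a future trial, calls its findings not definitive, and reserves full power for a range of outcomes to the later study. That stands, and it limits the consequence. It does not supply a criterion: the same paragraph foresees a demonstration of effectiveness, and the analysis section promises p-values and claims power for primary outcomes.

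The contrast is also not wholly open, since the model section specifies the treatment x time interaction and the power statement rests on it. That stands too. The score remains unnamed, and the non-linear contrasts are not ranked against the interaction.

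A reader might infer that an effectiveness claim carries up to about a 50% false-positive risk. The documents do not support that. The figure counts results in either direction, whereas a false claim for RISE needs a result in its favour. It assumes independence, which is implausible for overlapping symptom scales such as CES-D, PCL-5 and the DASS anxiety subscale. It is not a ceiling either, because subscales and extra contrasts raise it. A reader might also infer that the plan tests at least 14 scales, or treats any single significant scale as success. The plan speaks of psychosocial outcomes without listing them, and it states no success rule of any kind.

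**Conclusion.** The concern holds in this form: primary outcomes are invoked and powered for, but no primary score or contrast is named, and there is no alpha, multiplicity rule or success criterion, while an effectiveness conclusion is anticipated. This is more than a missing definition, because a primary chosen after the data are seen biases the conclusion.

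The size depends on the assumptions in step 3 of the working. The figure relevant to a false claim for RISE is about 28-30% under independence and 12-22% at correlations of .7 to .3, for 13 or 14 scales with one test each. Even the lowest of these is nearly five times the 2.5% of a single test (12/2.5 = 4.8). The absence of a named primary needs none of these assumptions; it can be read directly from the document.

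**What to change.** Before any comparative analysis:

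1. Name one primary score and one primary contrast from the multilevel model already planned, for example the treatment x time interaction on which the power statement rests. State the alpha and sidedness. Substituting a different contrast, such as a difference at 10 weeks, would need its own power calculation.
2. State that RISE will be said to demonstrate effectiveness only on that test.
3. If empowerment is chosen, note that the RISE arm also completes an empowerment measure at the start of every session and the comparison arm does not. The same applies to self-efficacy, patient activation and valued action.
4. Label all other scales, subscales and contrasts secondary. Report them as effect sizes with 95% intervals and no effectiveness claim, or with Holm-adjusted p-values if a claim is made.

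The cost is a few sentences of SAP text. The named primary test pays no multiplicity penalty. The downside is that a nominally significant secondary result will no longer count on its own as evidence of effectiveness.

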#### **(c) Method and Data Analysis**

##### Aim 3

**Randomized clinical trial (RCT):** The goal of Aim 3 is to test the RISE intervention in comparison to an information/referral condition for women VA patients who have experienced past-year IPV. We selected a Hybrid Type 1 RCT design to evaluate the initial effectiveness RISE while gathering information on barriers and facilitators of implementation. We selected an information/referral comparison condition because a) this intervention is consistent with the current standard of care at the two study sites (and in the community); b) many other VA facilities are supposed to provide information and referrals for women who disclose IPV (according to VHA recommendations); and 3) an information/referral condition conforms to the US Preventive Services guidelines and to the suggestions of the Department of Health and Human Services. Participants will receive the information/referral condition for up to 60 minutes in order to standardize the comparison condition while also ensuring that women receive at least the minimum standard of care. At VA Boston, up to 68 female patients will be recruited and randomly assigned. Assuming 15% loss to follow-up based on current study estimates, we will aim to enroll 68 women to ensure sample size of n=60 for participants with post-treatment and/or follow-up assessments (i.e., at least 2 data points). To address our sub-aim, providers will be invited to participate in brief (30-minute), semi-structured qualitative interviews toward the end of the RCT to provide perspective on RISE implementation.

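### The 118 degrees of freedom given for the treatment-by-time test count visits within women rather than women (about 58), and the plan names no random effects, covariance or df method

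*Combined protocol and SAP*

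**What the plan says.** Under Quantitative Data Analyses (Aim 3), the model paragraph codes the three visits 0, 1 and 2 and describes a two-level growth model: "We will add a dummy-coded intervention variable (RISE vs. information/referral condition) as a predictor of the Level-1 change parameters", those parameters being initial status and change over time. A further model with polynomial and orthogonal contrasts is also planned. Effect sizes with 95% confidence intervals are to be reported for all primary and secondary outcomes, partly to guide a future trial.

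The power paragraph in the same section counts 60 women, hence "time points = 180 measurement observations", or 204 with 68 women. It then says "The interaction term from the multilevel model will have 118 degrees of freedom, given the study design". The claimed power of .95 for the primary outcomes is drawn directly from that count.

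The visits are described under Female VHA Patient Assessments: "post-treatment assessment (i.e., 10-weeks post enrollment), and 1 month follow-up (i.e., 14 weeks post-enrollment". The Aim 3 method text allows for 15% loss and counts 60 "participants with post-treatment and/or follow-up assessments (i.e., at least 2 data points".

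The plan does not say whether the time slope is random, which within-woman covariance is used, or how the df are obtained. It gives no between-visit correlation and no slope variance.

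**The concern.** Arm is a property of the woman. If arm predicts each woman's rate of change, the evidence is one slope per woman in two groups, and the natural df are the number of women minus two. A figure of 118 instead counts visits within women as the unit of evidence. The two paragraphs therefore point to different error terms, and 118 is the only clue the plan gives about which one is meant.

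A random-intercept model assumes the same correlation between every pair of visits and no spread in women's slopes. The protocol gives reason to doubt both. RISE runs from one to six sessions with modules chosen by the patient, against a single comparison session, so uneven individual change is likely by design. Scores taken closer together in time usually agree more closely. When the assumption fails in that direction, the standard error of the treatment-by-time term is too small. The p-values and the 95% intervals for the effect sizes then look more certain than they are.

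**Working it through.** **Inputs from the plan.** 60 women, 3 visits, time codes 0/1/2, visits at 0, 10 and 14 weeks, 118 df, power .95. **Assumed.** 30 women per arm, two-sided 5%, complete data, and the correlations below.

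**1. Reproducing 118.** 60 × 3 = 180 observations; 180 - 60 woman intercepts - 2 within-woman terms (time, arm × time) = 118. With 68 women, 204 - 68 - 2 = 134. The subject-level count is 60 - 2 = 58, or 68 - 2 = 66.

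**2. Reproducing .95.** The power paragraph also gives a proportion of variance (PV) of .10. Noncentrality 118 × .10/.90 = 13.1 on F(1, 118) gives power .949, so the stated figure reproduces. The same convention with 58 df gives 58 × .10/.90 = 6.4 and power about .70. The loss comes from using the df as the multiplier of the effect: with noncentrality held at 13.1, 58 df gives .945.

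**3. What a random-intercept test does.** With codes 0/1/2, each woman's slope depends on visit 3 minus visit 1. Take unit variance and let r12, r13, r23 be the correlations of the three visit pairs. The normalised linear and quadratic contrasts have variances

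- V_L = 1 - r13
- V_Q = 1 - (2·r12 + 2·r23 - r13)/3

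The slope difference should be judged against V_L, on 58 df. The random-intercept model judges it against the pooled value (58·V_L + 60·V_Q)/118. Here 58 + 60 = 118, which shows where the extra df come from. The ratio of model SE to true SE is √(pooled/V_L).

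- Equal correlations of .6: V_L = .400, V_Q = .400, ratio 1.00.
- Stable trait .4, measurement error .2, and a decaying part .4 with 4-week correlation .8 (r = .63/.58/.72): V_L = .417, V_Q = .295, pooled .355, ratio .92.
- Pure exponential decay, 4-week correlation .8 (r = .57/.46/.80): V_L = .542, V_Q = .238, pooled .387, ratio .845.
- r = .5/.6/.6: V_L = .400, V_Q = .467, pooled .434, ratio 1.04 (conservative).

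**4. Simulated type I error** (40,000 null trials per case; simulation standard error about 0.1 percentage point at 5%).

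| Within-woman pattern | Random intercept, 118 df |
|---|---|
| r = .5/.6/.6 | 4.2% |
| Equal correlations | 5.1% |
| Stable trait + decay + measurement error | 5.8-7.3% |
| r = .6/.5/.7 | about 8% |
| Pure decay, 4-week correlation .3 / .5 | 6.2 / 7.7% |
| Pure decay, 4-week correlation .7 / .8 / .9 / .95 | 9.2 / 9.5 / 10.2 / 10.7% |
| Random slopes, 14-week slope variance .1 / .25 / .5 / 1.0 / 2.0 (intercept variance .6, residual .4) | 5.7 / 6.5 / 7.8 / 9.3 / 11.1% |

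A t-test on individual slopes with 58 df stays at 4.6-5.2% in every case.

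**5. Is the visit spacing the cause?** With equal spacing (0, 7, 14 weeks) and the same decay of .7/.8/.9, the random-intercept test runs at 8.6/9.5/10.1%, against 9.2/9.5/10.2% for the actual schedule. The spacing adds little.

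**6. Do the df alone matter?** Critical t is 1.980 on 118 df and 2.002 on 58. A test with the correct SE but referred to 118 df has a true level of 5.24%.

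**The case against.** The strongest reply is that 118 does not identify the model. A between-within df rule gives 118 to a within-woman term even when a random slope is fitted. The SE would then be right and the level about 5.2%. The number also equals (60 - 1) × (3 - 1), a repeated-measures count, and the power paragraph mentions traditional repeated-measures methods. It appears only in that paragraph. The model paragraph, which governs the analysis, reads naturally as allowing random slopes. All of this stands. A reader might infer that the plan commits to a random-intercept model; the documents do not say so.

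A reader might also infer that the 5% test will run at 9-10%, about double the stated rate. That needs near-pure decay with a 4-week correlation of about .7 or more, or a slope variance over 14 weeks at least 2.5 times the residual variance (1.0/.4). The documents give no such figures, and self-report scales usually carry a stable component and measurement error. If both arms improve by 1 SD by week 10 and then level off, the 9.5% case falls to 6.8%, because the straight-line model puts the curvature into the residual.

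Nor can the 0/10/14-week schedule carry the blame: equal spacing gives nearly the same result.

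The simulations also use complete data, whereas the plan allows for 15% loss and for women with only two assessments.

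What survives is that the plan states a df figure counting visits within women, next to a model whose treatment comparison is between women, and specifies nothing that would settle which error term applies.

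**Conclusion.** The point holds as a mismatch with a specification gap, and should be fixed. The 118 is the within-woman residual count; the subject-level df for arm predicting individual change are about 58, or 66 with 68 women. If the analysis used a random intercept only, the true level of a nominal 5% test would lie between about 4% and 11%. It is 5% under equal correlations, about 6-8% under mixed patterns of stable trait, decay and measurement error, and 9% or more only at the extremes. The driver is unequal correlation or varying slopes. If a random slope or unstructured covariance is what the team intends, the 118 does almost no harm to the error rate, but the power of .95 derived from it still needs restating. These sizes rest on assumed correlations, equal arms and complete data.

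**What to change.** In the model paragraph, state that the three visits have an unstructured within-woman covariance, fitted by REML, with Kenward-Roger or Satterthwaite df. In the power paragraph, replace 118 with about 58 (60 women) or 66 (68 women), noting that missing visits lower it, and restate the power that was drawn from it.

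The cost is two or three sentences and a standard software option. Intervals become slightly wider. If correlations are in fact equal, the change is about 1% (2.002/1.980 = 1.011). If correlation decays strongly, it is more, for example 1.011/.845 = 1.20 times as wide in the pure-decay case with 4-week correlation .8. That extra width is the uncertainty a random-intercept model would have hidden.

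### The power paragraph gives d=.5 and f²=.15 as the same effect when they are not, and the stated power of .95 does not follow from d=.5

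*Combined protocol and SAP*

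**What the plan says.** Quantitative Data Analyses (Aim 3) argues that RISE adds to standard care, "so it is expected that the effect will be modest", and gives that effect in one bracket as d=.5, f²=.15 and PV=.1. On the interaction test it then states that the term "will have 118 degrees of freedom, given the study design, which is more than sufficient to render a power = .95"; this claim is made about the primary outcomes. A second route is mentioned: "A simulation was also conducted leveraging the inputs from the prior studies, assuming a modest effect size", with power above .80 in every condition.

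The test is the treatment-by-time interaction, with this coding: "Time will be coded as 0, 1, and 2 respectively for pretreatment, posttreatment, and 1-month follow-up". Quadratic and orthogonal contrasts are also planned.

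The documents give no alpha, no numerator degrees of freedom, no scale for d, no between-visit correlation and no list of simulation inputs.

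**The concern.** The three figures are offered as equivalents, but on the usual conversion d=.5 and f²=.15 differ 2.4-fold in f² (.15/.0625). A reader cannot tell whether the trial was planned for d=.5 or for about d=.77, and power differs greatly between the two.

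The practical risk lies in interpretation. If the interaction is not significant, a reader who takes the paragraph at face value would treat the result as strong evidence against d=.5, because the plan claims power of .95 for an effect it labels d=.5. The same ambiguity affects the simulation: its effect is described only as modest, which is the word whose value is unclear.

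**Working it through.** **Inputs.** From the plan: d=.5; f²=.15; PV=.1; 60 analysed women (up to 68); three visits; time coded 0, 1, 2; 118 df; power .95. Assumed: two-sided alpha .05 (in line with the planned 95% intervals), 1:1 allocation, equal correlation ρ between visits, complete data.

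**1. The 118 df.** 60 × 3 = 180 observations; 180 − 60 − 2 = 118. For 68 women, 204 − 68 − 2 = 134. The df figure is not an error.

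**2. Conversions.** For two equal groups, f² = d²/4 and PV = f²/(1+f²).

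| Stated figure | d | f² | PV |
|---|---|---|---|
| d=.5 | .50 | .0625 | .059 |
| PV=.1, taken as .10 | .67 | .111 | .10 |
| f²=.15 | .77 | .15 | .13 |

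Rounding does not close the gap between d and f²: d from .45 to .55 gives f² from .051 to .076. PV=.1, printed to one decimal, is compatible with either .059 or .13.

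**3. Reproducing .95.** Noncentral F with 1 and 118 df, noncentrality λ = f² × 118 to f² × 120:

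| Input | λ | Power |
|---|---|---|
| PV=.10 | 13.1 to 13.3 | .949 to .952 |
| f²=.15 | 17.7 to 18.0 | .987 to .988 |
| d=.5 | 7.4 to 7.5 | .768 to .775 |

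PV=.10 reproduces the plan's figure, and f²=.15 meets it as a floor. d=.5 does not, even at two-sided alpha .10 (.854 to .859). At alpha .01, f²=.15 gives .942 to .946. The .77 for d=.5 shows only where .95 did not come from. It is not this trial's power, because this calculation ignores the correlation between visits.

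**4. Power of the planned test at d=.5.** Read d as the arm difference in change at the last visit, in SD units. With equally spaced coding the linear contrast is last visit minus baseline, so the SD of change is √(2(1−ρ)) and the standard error is √(2(1−ρ) × 2/n) for n per arm. At n=30 and ρ=.5 this is √(2/30) = .258; the noncentrality is .5/.258 = 1.94, and the noncentral t on 58 df gives .48. The more favourable contrast takes the mean of both later visits minus baseline, with d=.5 at both; 2(1−ρ) becomes 1.5(1−ρ).

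| Contrast, n per arm | ρ=.3 | ρ=.5 | ρ=.7 | ρ=.8 | ρ needed for .95 |
|---|---|---|---|---|---|
| Linear, 30 | .36 | .48 | .69 | .85 | .86 |
| Linear, 34 | .40 | .53 | .75 | .90 | .84 |
| Mean of later visits, 30 | .46 | .59 | .81 | .94 | .81 |
| Mean of later visits, 34 | .51 | .65 | .86 | .96 | .79 |

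For power .80, the linear test needs ρ of about .77 (30 per arm) or .74 (34 per arm). Simulating the random-intercept test for 60 women on 118 df (20,000 runs per cell) gave .36, .48, .70 and .86 across the four correlations, and .95 at ρ=.86. The choice of 58 or 118 df therefore hardly matters.

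**5. If the effect is d=.77.** The linear test with 30 per arm gives .70, .84, .97 and .997 at the same correlations, and passes .80 from ρ of about .45.

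**6. Other scales that might reconcile the figures.**
- *f² and PV as partial within-woman effects of the linear test.* λ = .25 × 15/(2(1−ρ)) and f² = λ/118. Then d=.5 equals PV=.10 only at ρ≈.86 and f²=.15 only at ρ≈.89.
- *d in raw SD units, f² and PV on the change score at the last visit.* ρ = 1 − (.5/d*)²/2, where d* is the change-score effect: .72 for d*=.67 and .79 for d*=.77. With 30 per arm these effects give power .72 and .84, so .95 is still not reached.
- *f=.25 (that is, d/2) taken as the interaction effect itself in a repeated-measures formula.* λ = f² × 180/(1−ρ) on 2 and 116 df gives .953 at ρ=.3. The interaction f per unit of d is .2041 for an arm difference of 0, d/2, d and .2357 for 0, d, d. So f=.25 there means d=1.22 or d=1.06, not .5.

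**7. What the sample can deliver (linear test).**

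| | ρ=.3 | ρ=.5 | ρ=.7 |
|---|---|---|---|
| Detectable d at power .80, N=60 | .87 | .74 | .57 |
| Detectable d at power .80, N=68 | .82 | .69 | .53 |
| 95% CI half-width, N=60 | .61 | .52 | .40 |
| 95% CI half-width, N=68 | .57 | .48 | .38 |

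**The case against.** The strongest reply is that .95 does reproduce: PV=.10 on 118 df gives it, and f²=.15 exceeds it, which fits the claim that the df are more than sufficient. That stands. The fault is that the paragraph calls the same effect d=.5 and does not say which figure was used.

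Second, the conversion assumes a scale that the plan leaves open, and d in raw SD units can match the other figures on the change-score scale at correlations of .72 to .79. That is fair, but the plan states neither the scale nor a correlation, and this reading still gives only .72 to .84 with 30 per arm.

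Third, the simulation may have used a suitable correlation from prior studies. It may; the result above .80 is not shown to be wrong, only impossible to check.

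Fourth, the consequences are limited. The plan reports effect sizes with 95% intervals, "To examine the range of effect sizes that might be reasonable to expect in a future trial", and the discussion of generalizability says of the findings that "they will not be definitive". This stands and limits the point to reporting. It does not make an unqualified .95 correct.

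**Conclusion.** The point holds. As printed, d=.5 and f²=.15 are different effects under the standard two-group conversion, and .95 corresponds to PV=.10 (d=.67) or more, not to d=.5. For the arm difference in change, d=.5 reaches .95 only at a between-visit correlation of about .79 to .86, depending on contrast and on 60 or 68 women. At a correlation of .5, power at d=.5 is .48 to .65 over the same cases.

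These values rest on two-sided alpha .05, 1:1 allocation, equal correlations and complete data. The last is favourable, since the 60 are women with at least two assessments rather than all three. The trial is not shown to be underpowered, because the true correlation is unknown. This is a reporting error in one paragraph that should be corrected; it does not undermine the design.

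**What to change.** Rewrite the power paragraph in Quantitative Data Analyses (Aim 3):

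- State one effect on one defined scale, for example the arm difference in change in baseline SD units, and drop or correctly convert the other two figures.
- State alpha and sidedness, the time contrast that is powered, and the assumed range of between-visit correlation.
- Replace the .95 with the power those inputs give for 60 and 68 women. Alternatively, give the detectable effect at power .80 and the expected 95% interval width, for example about d=.74 and a half-width of .52 for 60 women at an assumed correlation of .5.
- Report the effect size, correlation, alpha and conditions behind the simulation so that its result can be checked.

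The cost is one paragraph, with no added patients and no change of test. The downside is a less favourable stated power.
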